6.2.3.2 Guidelines for the follow-up of laboratory liver abnormalities

In patients with any clinically relevant laboratory liver abnormality, as defined below, hepatic toxicity monitoring must include **ALL** of the following liver function tests (LFTs): albumin, ALT, AST, total bilirubin (fractionated if total bilirubin $> 2.0 \times$ ULN), indirect bilirubin, alkaline phosphatase (fractionated if alkaline phosphatase is grade 2 or higher), creatine kinase, prothrombin time (PT) or INR and GGT. Note: for patients with Gilbert Syndrome, total and direct bilirubin must be monitored, but intensified monitoring applies to changes in direct bilirubin only. (See Table 12) In case of any occurrence of ALT/AST/total bilirubin increase to grade 2 the LFTs must be monitored weekly (or more frequently if clinically indicated) until the event resolves to \leq grade 1. Thereafter monitoring must be continued every 2 weeks (or more frequently if clinically indicated) for two additional cycles (e.g. 6 weeks). If there is no recurrence of \geq grade 2 ALT/AST/total bilirubin elevations during this period, subsequent monitoring must be performed every 3 weeks.

In case of any occurrence of ALT/ AST/ bilirubin increase to grade 3 or 4, LFTs must be monitored weekly (or more frequently if clinically indicated) until the event resolves to \leq grade 1. Thereafter monitoring must be continued every 2 weeks (or more frequently if clinically indicated) for four additional cycles (e.g. 12 weeks). If there is no recurrence of \geq grade 2 ALT/AST/total bilirubin elevations during this period, subsequent monitoring must be performed every 3 weeks.

Patients who discontinue ribociclib+everolimus treatment due to liver toxicity must be monitored weekly (or more frequently if clinically indicated) until the event resolves to \leq grade 1 or stabilization occurs (no CTCAE grade change over 3 weeks). (See Table 12)

6.2.3.3 Guidelines for the follow-up of laboratory renal abnormalities

In case of any occurrence of serum creatinine results of grade 2 or greater, tests must be performed weekly (or more frequently if clinically indicated) until the event resolves to \leq grade 1. Subsequent monitoring must be performed every 3 weeks.

In case of any occurrence of serum creatinine \geq grade 3, tests must be performed twice weekly (or more frequently if clinically indicated) until the event resolves to \leq grade 1. Subsequent monitoring must be performed every 3 weeks. (See Table 12)

6.2.3.4 Guidelines for the treatment of study drug induced diarrhea

Mild to moderate diarrhea has been observed frequently in patients treated with ribociclib. Patients should be monitored for diarrhea and given appropriate supportive care with diagnostic or therapeutic intervention, including interruption of therapy with ribociclib as appropriate. If a patient has experienced ribociclib-related diarrhea, and it is considered

sufficiently severe to warrant the use of prophylactic anti-diarrhea therapy, then prophylaxis may be instituted in that patient with subsequent treatment.

6.2.3.5 Guidelines for the treatment of study drug induced nausea and vomiting

Preclinical studies have identified vomiting as an AE of ribociclib administration in dogs. Nausea and vomiting are the most common non-hematologic adverse reactions observed with ribociclib; the majority of cases are mild to moderate. Hence, prophylactic treatment with anti-emetics is not required when starting therapy with ribociclib. However, all patients should be carefully monitored for the development of nausea and/or emesis, and if they occur, treatment with anti-emetics may be instituted. If a patient has experienced ribociclib-related nausea and/or vomiting, and it is considered sufficiently severe to warrant the use of prophylactic anti-emetic therapy, then prophylactic therapy may be used in that patient with subsequent treatment.

Table 12 Follow-up evaluations for selected toxicities

Toxicity	Follow-up evaluation*
Investigations (hematologic)	Febrile neutropenia, neutropenia or thrombocytopenia \geq CTCAE Grade 3 Test weekly (or more frequently) until \leq Grade 2 Subsequent monitoring must be performed every 3 weeks
Investigations (hepatic)	Total ALT/AST/total bilirubin Grade 2: Test weekly (or more frequently) until \leq Grade 1 Thereafter, continue to test every 2 weeks (or more frequently) for 2 cycles (6 weeks). If no recurrence of \geq Grade 2 event, continue monitoring every cycle (3 weeks) Total ALT/AST/total bilirubin \geq Grade 3: Test weekly (or more frequently) until \leq Grade 1 Thereafter, continue to test every 2 weeks (or more frequently) for 4 cycles (12 weeks). If no recurrence of \geq grade 2 event, continue monitoring every cycle (3 weeks) Discontinuation due to liver toxicity: Test weekly (or more frequently) until \leq Grade 1 or stabilization
Investigations (renal)	Serum creatinine Grade 2: Test weekly (or more frequently) until Grade 1 Thereafter, test every cycle (3 weeks) Serum creatinine \geq Grade 3: Test twice weekly (or more frequently) until \leq Grade 1 Thereafter, test every cycle (3 weeks)
Investigations (Metabolic)	Hyperglycemia \geq Grade 3 Test weekly (or more frequently) until Grade 1

*Note: this table refers only to the evaluation schedule to monitor selected toxicities. Refer to [Table 11 Criteria for post-tumor resection interruption and re-initiation of ribociclib+everolimus treatment](#)

6.3 Concomitant medications

In general, the use of any concomitant medication/therapy deemed necessary for the care of the patient (e.g., anti-emetics, anti-diarrheal agents) is permitted, except when specifically prohibited. Anesthesia may use medications that would otherwise be prohibited when deemed clinically necessary, but if possible should be avoided.

The patient must be told to notify the investigational site about any new medications he/she takes after the start of the ribociclib+everolimus treatment. All medications, including herbal/natural medications (excluding ribociclib treatment and prior antineoplastic treatments and blood

transfusions), surgeries and procedures (including physical therapy) administered within 28 days prior to the first dose of administration of ribociclib treatment through 30 days after the last dose of treatment will be recorded. Medications include not only physician prescribed medications, but also all over-the counter (OTC) medications, herbal medications (prohibited, see [Section 6.3.3](#)), food or vitamin supplements, and blood transfusions.

For up to date information on prohibited medications please refer to the following websites:

- Medication with a known risk of prolonging the QT interval or inducing Torsades de Pointes (please refer to <http://www.acert.org/medical-pros/drug-lists/drug-lists.cfm>)
- Strong inhibitors or strong inducers of CYP3A4/5 (please refer to <http://medicine.iupui.edu/flockhart/table.htm> or <http://www.druginteractioninfo.org>)
- Medications with a low therapeutic index that are primarily metabolized by CYP3A4/5, CYP2C8 and/or CYP2C9 (please refer to <http://medicine.iupui.edu/flockhart/table.htm> or <http://www.druginteractioninfo.org>)

6.3.1 Permitted concomitant therapy

Medications required to treat AEs, manage cancer symptoms, concurrent diseases and supportive care agents, such as pain medications, anti-emetics and anti-diarrheal are allowed.

The patient must be told to notify the investigational site about any new medications he/she takes after the start of the study treatment. All medications (other than study drugs) and significant non-drug therapies (including vitamins, herbal medicines, physical therapy and blood transfusions) administered within 30 days of study entry and during the study must be listed on the Concomitant medications/Significant non-drug therapies eCRF.

If patients take concomitant medications chronically, any change in dose schedule of concomitant medication throughout the study period should be clearly documented.

6.3.1.1 Palliative radiotherapy

In Phase 2 Palliative radiation is permitted. It should not be delivered to a target lesion and it should not encompass more than 25% of irradiated bone marrow.

If palliative radiotherapy is initiated after the start of study treatment, the reason for its use must be clearly documented and progression as per RECIST 1.1 must be ruled out.

No dose modification of study treatment is needed during palliative radiotherapy.

Refer to the ribociclib Investigators Brochure and other drug package insert and [Appendix 2](#) for information on possible interactions with other drugs.

6.3.1.2 Use of antiemetic medications

Ribociclib has low to minimal emetogenic potential according to a definition of antineoplastic agent emetogenicity ([Grunberg et al, 2010](#)). Antiemetic therapy can be used according to clinical guidelines for antineoplastic medications with low to minimal emetogenic potential for treatment and/or prevention of nausea and vomiting as a result of study treatment (NCCN Clinical Practice Guidelines in Oncology. Antiemesis, 2016; [Roila F et al, 2016](#)).

Potential drug interaction between ribociclib/placebo and antiemetic medications should always be taken into consideration. Example of prohibited antiemetic medication is intravenously administered ondansetron that in combination with ribociclib may precipitate TdP. Refer to Sections 6.3.1, 6.3.2 and 6.3.3 for list of medications that are prohibited or allowed to be used with ribociclib+everolimus.

If a clinical decision to use ondansetron is made in order to treat the patient, this will be recorded in the concomitant medications but will not be recorded as a deviation. Efforts to not utilize ondansetron should be made.

6.3.2 Permitted concomitant therapy requiring caution and/or action with ribociclib

Medications to be used with caution during ribociclib and everolimus in this study are listed below (see [Appendix 2](#)). This list is not comprehensive and is only meant to be used as a guide. These medications should be excluded from patient use if possible. If they must be given, then use with caution and consider a ribociclib interruption if the concomitant medication is only needed for a short time.

- Moderate inhibitors or inducers of CYP3A4/5 (may increase or decrease ribociclib exposure, respectively)
- Moderate P-gp inhibitors and inducers
- Sensitive substrates of CYP3A4/5 that do not have narrow therapeutic index (ribociclib may increase exposure to these medications)
- Strong inhibitors of BSEP (based on in vitro data co-administration with ribociclib may lead to intrahepatic cholestasis)
- Medications that carry a possible risk for QT prolongation (may precipitate QT prolongation and TdP)
- Sensitive substrates of the renal transporters, MATE1, OCT2 and BCRP (has a potential to increase exposure to substrates of these transporters, although no animal or clinical data are available to support these statements)

6.3.2.1 Hematopoietic growth factors

Prophylactic use of WBC growth factors with ribociclib is not recommended.

6.3.2.2 Corticosteroids

Chronic dosing of corticosteroids such as dexamethasone and prednisone is known to lead to induction of CYP3A enzymes, thereby potentially increasing the risk of reducing ribociclib drug exposure to subtherapeutic levels. Systemic corticosteroid treatment should not be given during the study, except for:

- Topical applications (e.g., rash), inhaled sprays (e.g., obstructive airways diseases), eye drops or local injections (e.g., intra-articular);
- A short duration (< 5 days) of systemic corticosteroids \leq to the anti-inflammatory potency of 4 mg dexamethasone (e.g. for chronic obstructive pulmonary disease, or as an antiemetic);

- Patients may be given dexamethasone alcohol-free mouthwash when starting everolimus treatment prophylactically for stomatitis;
- As determined by the investigator for clinical treatment.

Corticosteroid usage for CNS-related symptoms must be recorded, but are allowed.

6.3.2.3 Drugs that are metabolized by CYP450 enzymes

In vitro drug metabolism studies show that the metabolism of ribociclib is mediated by P450 enzymes CYP1A2, CYP2E1, and CYP3A4. Ribociclib is a time-dependent CYP3A4/5 inhibitor. Clinical studies have not yet been performed to confirm the potential effect of ribociclib on substrate drugs metabolized by these enzymes in patients.

Concomitant treatment of ribociclib with weak inhibitors or inducers of CYP3A4/5 is permitted. Caution is advised when ribociclib is co-administered with drugs that are moderate inhibitors or inducers of CYP3A4/5 ([Appendix 2](#)). Duration of concomitant treatment should be kept as short as possible, or completely avoided whenever possible. Patients receiving such medications must be monitored closely for any potentiation of toxicity or decrease of clinical benefit due to any individual concomitant medications, and may require dose titration or adjustment. Note that co-administration of ribociclib with strong inducers of CYP3A4/5 is prohibited ([Section 6.3.3.4](#)).

Concomitant treatment of ribociclib with medications known to be metabolized by CYP1A2 and CYP2E1 is allowed with caution ([Appendix 2](#)), except for drugs which have narrow therapeutic index/sensitive substrates for these CYP isoforms ([Section 6.3.3.5](#) and [Appendix 2](#)).

6.3.2.4 Gastric protection agents

The use of gastric protection agents including antacids, H2-antagonists, and proton pump inhibitors (PPIs; [Appendix 2](#)) is allowed.

6.3.3 Prohibited concomitant therapy with ribociclib and everolimus

Patient must be able to stop receiving any of the following medications 7 days prior to starting study drug:

- Known strong inducers or inhibitors of CYP3A4/5, including grapefruit, grapefruit hybrids, pomelos/pummelos, star-fruit, pomegranates or pomegranate juice and Seville oranges.
- That have a narrow therapeutic window and are predominantly metabolized through CYP3A4/5.
- Strong P-gp inhibitors and inducers.
- Herbal preparations/medications, dietary supplements known as strong inhibitors or inducers of CYP3A4 or those with a known risk of QT prolongation.
- Concomitant use of medication(s) with a known risk to prolong the QT interval and/or known to cause Torsades de Pointe that cannot be discontinued (within 5 half-lives or 7 days prior to starting study drug) or replaced by safe alternative medication are exclusionary to participation.

6.3.3.1 Other anticancer therapy

Anticancer therapy (chemotherapy, targeted therapy, biologic therapy, or radiation therapy (except palliative radiotherapy as described in [Section 6.3.1.1](#)), and anti-cancer surgery) other than the ribociclib treatment must not be given to patients while they are enrolled in the treatment trial (i.e.: during the initial 5-day regimen). If such agents are required then the patient must be permanently discontinued from the treatment portion of the study.

6.3.3.2 Hematopoietic growth factors

Hematopoietic growth factors may be used according to ASCO guidelines. (<http://jco.ascopubs.org/content/early/2015/07/08/JCO.2015.62.3488.full>)

6.3.3.3 Other investigational therapies

Other investigational therapies must not be used while the patient is on the study.

6.3.3.4 Strong CYP3A inhibitors and inducers

In vitro metabolism studies suggest that oxidative metabolism of ribociclib is predominantly mediated by CYP3A4/5.

Strong inhibitors or inducers of CYP3A4/5 are prohibited, with the exception of phenytoin and carbamazepine. Patients receiving other concomitant medications known to strongly inhibit and/or induce CYP3A4/5 that are deemed medically necessary should be excluded from the study. Refer to [Appendix 2](#) for a list of these medications. Please note that this list may not be comprehensive. Patients should stop using medications at least 7 days prior to first dose of treatment.

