 - Concomitant use of medication(s) with a known risk to prolong the QT interval and/or known to cause Torsades de Pointe that cannot be discontinued (within 5 half-lives or 7 days prior to starting study drug) or replaced by safe alternative medication.
 - Inability to determine the QT interval on screening (QTcF, using Fridericia's correction).
 - Systolic blood pressure (SBP) >160 mmHg or <90 mmHg at screening (may be repeated up to 2x).
20. Patient is currently receiving any of the following medications and cannot be discontinued 7 days prior to starting study drug (see [Appendix 2](#) for details):
 - Known strong inducers or inhibitors of CYP3A4/5, including grapefruit, grapefruit hybrids, pomelos/pummelos, star-fruit, pomegranates or pomegranate juice and Seville oranges.
 - That have a narrow therapeutic window and are predominantly metabolized through CYP3A4/5.

- Herbal preparations/medications, dietary supplements known as strong inhibitors or inducers of CYP3A4 or those with a known risk of QT prolongation. (Does not include Ca, Mg, Vit D or KCl supplements).

- Known strong inhibitors or inducers of P-gp.

21. Patients taking ACE inhibitors.
22. Patient is currently receiving warfarin or other coumarin-derived anticoagulant for treatment, prophylaxis or otherwise. Therapy with heparin, low molecular weight heparin (LMWH) or fondaparinux is allowed.
23. Participation in a prior investigational study within 30 days prior to enrollment or within 5 half-lives of the investigational product, whichever is longer.
24. Patient has had major surgery within 14 days prior to starting study drug or has not recovered from major side effects (tumor biopsy is not considered as major surgery).
25. Patient has not recovered from all toxicities related to prior anticancer therapies to NCI-CTCAE version 4.03 Grade ≤ 2 (Exception to this criterion: patients with grade 1 taxane-induced neuropathy, any grade of alopecia, amenorrhea or other toxicities not considered a safety risk for the patient as per investigator's discretion, are allowed to enter the study.).
26. Patient with a Child-Pugh score B or C.
27. Patient has a history of non-compliance to medical regimen or inability to grant consent.
28. Pregnant or nursing (lactating) women, where pregnancy is defined as the state of a female after conception and until the termination of gestation, confirmed by a positive hCG laboratory test.

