Appendix 1: ECOG Performance Status Scale

ECOG Performance Status Scale	
Grade	Descriptions
0	Fully active, able to carry on all pre-disease performance without restriction
1	Restricted in physically strenuous activity, but ambulatory and able to carry out work of a light or sedentary nature (e.g., light housework, office work)
2	Ambulatory and capable of all self-care, but unable to carry out any work activities Up and about more than 50% of waking hours
3	Capable of only limited self-care, confined to bed or chair more than 50% of waking hours
4	Completely disabled Cannot carry on any self-care Totally confined to bed or chair
5	Dead

Appendix 2: List of prohibited concomitant medications and concomitant medications requiring caution

Table 16 Prohibited medications that are strong inducers or inhibitors of CYP3A, or CYP3A substrates with narrow therapeutic index

Category	Drug Name
Strong CYP3A4/5 inhibitors	Atazanavir/ritonavir, boceprevir, clarithromycin, cobicistat, conivaptan, danoprevir/ritonavir, darunavir/ritonavir, elvitegravir/ritonavir, grapefruit juice, idelalisib, indinavir, indinavir/ritonavir, itraconazole, ketoconazole, lopinavir/ritonavir, mibefradil, nefazodone, nelfinavir, omibitasvir/paritaprevir/dasabuvir/ritonavir (VIEKIRA PAK), posaconazole, ritonavir, saquinavir/ritonavir, telaprevir, telithromycin, tipranavir/ritonavir, troleandomycin/voriconazole
Strong CYP3A4/5 inducers	Apalutamide, carbamazepine ³ , enzalutamide, lumacaftor, mitotane, phenobarbital, phenytoin ³ , rifabutin, rifampin (rifampicin) ³ , St. John's wort (hypericum perforatum) ^{2,3}
CYP3A4/5 substrates with NTI ¹	Alfentanil, astemizole, cisapride, cyclosporine, diergotamine (dihydroergotamine), ergotamine, fentanyl, lomitapide ⁵ , lovastatin, nicardipine, nisoldipine, pimozide, quinidine, simvastatin, sirolimus, tacrolimus

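### Section 6.3.3.4 exempts phenytoin and carbamazepine from the strong CYP3A4/5 inducer ban, but Table 16 lists both as prohibited, and exclusion 20 and the Section 6.3.3 lead-in make no exception

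*Combined protocol and SAP*

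**What the plan says.** Section 6.3.3.4 sets the rule and its exception in one sentence: "Strong inhibitors or inducers of CYP3A4/5 are prohibited, with the exception of phenytoin and carbamazepine". It says that patients who need other strong inhibitors or inducers should be excluded, and sends the reader to Appendix 2 for the list.

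That list is Table 16 in Appendix 2 (numbered 17 in the list of tables), titled "Prohibited medications that are strong inducers or inhibitors of CYP3A, or CYP3A substrates with narrow therapeutic index". Its strong-inducer row begins "Apalutamide, carbamazepine" and continues "enzalutamide, lumacaftor, mitotane, phenobarbital, phenytoin". The only footnote on either drug marks it as a P-gp inducer.

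Exclusion 20 in Section 5.3 opens "Patient is currently receiving any of the following medications and cannot be discontinued 7 days prior to starting study drug", refers to Appendix 2 for details, and lists "Known strong inducers or inhibitors of CYP3A4/5, including grapefruit, grapefruit hybrids" and further items, with no exception. The lead-in to Section 6.3.3 repeats the class rule, again with no exception. Section 6.3.2.3 adds: "Note that co-administration of ribociclib with strong inducers of CYP3A4/5 is prohibited", and cites Section 6.3.3.4 as its source.

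On analysis, Section 9.7.1 defines a positive PK effect as each drug's unbound concentration in non-enhancing tumour exceeding its in vitro IC50. Section 9.7 summarises concentrations by time interval and overall. Section 9.6.1 rules out a separate SAP.

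**The concern.** Eligibility and permitted medication should not depend on which page a site consults. The trial allows up to three sites, and two of them could decide differently on the same patient while each follows the protocol.

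The conflict also bears on a primary endpoint. Section 6.3.3.4 describes ribociclib as metabolised mainly by CYP3A4/5, and Section 1.2.2.2.1 describes everolimus as metabolised almost only by CYP3A4. Section 6.3.2.2, on corticosteroids, accepts that CYP3A induction may push ribociclib exposure too low. A patient on phenytoin or carbamazepine could therefore fall below the IC50 threshold because of the co-medication rather than the dose. Nothing in the analysis would show this: Sections 7.1.1.1, 9.7 and 9.7.1 contain no stratum, covariate, exclusion or sensitivity analysis for such patients. The abbreviations list defines enzyme-inducing and non-enzyme-inducing anti-epileptic drugs, but the readable body text never uses either term.

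**Working it through.** The plan attaches no figure to this point, so there is nothing to reproduce. The check sets the texts side by side and then follows the PK result to the decisions it serves.

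**1. The texts**

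| Place | Scope | Names the two drugs? | Exception? |
|---|---|---|---|
| 6.3.3.4 | Strong inhibitors and inducers | Yes, as exempt | Yes |
| Appendix 2, Table 16 | Prohibited list | Yes, as prohibited | No |
| Exclusion 20 | Class, at entry, if it cannot be stopped 7 days before dosing | Through Appendix 2 | No |
| 6.3.3 lead-in | Class, 7-day stop | No | No |
| 6.3.2.3 | Class, with ribociclib | No | Unclear: cites 6.3.3.4 |

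**2. Test case.** Take a patient who cannot stop phenytoin.
- Under 6.3.3.4 the patient may enter and continue the drug.
- Under exclusion 20 the patient may not enter, and Section 5.1 requires that no exclusion criterion be met.
- A patient who can stop in time meets no conflict at entry. If either drug is started during treatment, 6.3.3.4 and Table 16 again disagree.

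**3. Where the PK result is used**
- Phase 2 entry (6.1.5): positive PK and PD are required, and PK is the main guide when PD is inconclusive.
- Optimal biological dose and expansion by 8 patients, 4 in each of time cohorts 1 and 3 (4.1.1, 6.1.2.1, Table 8).

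**4. Weight of one patient.** Share = 1/n, with n the number of patients at the level.
- n = 3: 1/3 = 33%.
- n = 6: 1/6 = 17%.
- After expansion, up to n = 14 (4.1.1): 1/14 = 7%. The decision to expand is taken before that, at 3 to 6 patients.

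**5. What cannot be computed.** The effect on the endpoint needs the fall in unbound tumour concentration under induction, the margin above IC50 without it, and the number of patients taking these drugs. The documents give none of the three.

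**The case against.** The strongest defence is that a specific exception overrides a general rule. The exemption looks deliberate, since the next sentence of 6.3.3.4 speaks of other strong inhibitors and inducers. Only Table 16 contradicts it by name. Section 6.3.2.3 cites the section that holds the exception and may import it, so it should not be counted as a clear conflict. Exclusion 20 and the 6.3.3 lead-in are class rules that may simply not have been updated. This narrows the conflict but does not remove it: 6.3.3.4 itself points to the list that prohibits both drugs, and the eligibility criterion carries no exception.

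Two stronger readings are tempting, and the documents do not support them.

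- **PK steers dose escalation.** Section 4.1.2 ties Phase 0 escalation to the Phase 0 DLT rules unless the DSMB decides otherwise, Table 8 escalates on DLT counts, and 6.1.2.1 continues escalation when PK and PD are positive and no DLT is seen. Section 2.3 shows that PK findings prompted later changes to the dose plan, but that is redesign, not the escalation rule.
- **The loss in a dose level's mean concentration can be stated as a percentage.** Any such figure needs an assumed induction size with no basis in the documents. It also concerns a mean by dose level, which Section 9.7 does not specify, while positivity is a threshold. For everolimus, 6.1.5 describes an opposing interaction (a simulated 3.5-fold rise in AUC with ribociclib), so the net effect is unknown.

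Two further points stand. The Phase 2 gate is individual: an induced patient below IC50 has been recorded at that patient's true exposure, so distortion arises only in inferences about the level. And a flag for strong inducers does not capture chronic corticosteroids, which 6.3.2.2 names as CYP3A inducers and allows for CNS symptoms.

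**Conclusion.** The inconsistency is real. It is direct and by drug name between 6.3.3.4 and Table 16, by class for exclusion 20 and the 6.3.3 lead-in, and ambiguous for 6.3.2.3. The same patient can be both permitted and excluded.

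The statistical consequence is narrower. An unflagged patient on one of these drugs would be pooled with the rest and would make up 17% to 33% of a level of 3 to 6 patients when the optimal biological dose and expansion are judged. Whether that patient would change a PK-positive count depends on whether induction moves the concentration across IC50, which the documents do not show. Confidence is high on the text conflict and limited on its effect on results. The analysis point matters mainly if the exemption stays or if such patients have already been treated.

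**What to change.** 1. Reconcile Section 6.3.3.4, Appendix 2 Table 16, exclusion 20 and the Section 6.3.3 lead-in so that they state one rule for phenytoin and carbamazepine, and conform 6.3.2.3. Which rule applies is for the sponsor and investigators to decide.
2. If the exemption stays, or if any patient already treated took either drug, add to Section 9.7 a flag for patients taking a strong CYP3A4/5 inducer at PK sampling, and report the PK and PD results with and without them. With 3 to 6 patients this is a descriptive display, not a comparison.
3. If the exemption is removed and no treated patient took either drug, step 2 is largely unnecessary.

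The cost is an amendment to wording and one flag in the PK and PD tables. Sections 6.3 and 6.3.1 already require concomitant medication to be recorded, so no new data are needed.
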